5 STUDY POPULATION

5.1 INCLUSION CRITERIA

All inclusion and exclusion criteria will be reviewed by the investigator or qualified designee to ensure that the participant qualifies for the trial.

In order to be eligible to participate in this study, an individual must meet all of the following criteria:

1. Provision to sign and date the consent form.
2. Participant must be ≥ 18 years of age
3. Histologically confirmed metastatic gastric or GEJ adenocarcinoma that is amenable to biopsy either at primary or metastatic site.
4. Patient must consent at initiation of study to serial tumor biopsies during study.
Irradiated lesions will not be considered for biopsy. For baseline biopsy, available archived tumor tissue of a metastatic tumor collected up to 28 days prior to registration is acceptable. If, after patient consent, the tumor is deemed inaccessible, the biopsy is not in the subject's best interest per investigator discretion, or the patient refuses biopsy during course of the study, patients will be allowed to remain on study.
5. Participant must have a primary tumor or a single metastatic site amenable to radiation in: the stomach, esophagus, liver, lungs, pancreas, thoracic/abdominal LNs, or soft tissues.
Of note - sites of disease planned to be biopsied should not be radiated.
6. Participant must have at least one radiographically-confirmed index lesion that will not undergo RT and is measurable based on RECIST v1.1.
7. Homologous recombination deficiency cohort: pre-identified presence of somatic or germline deleterious mutation, as determined by NGS only, in at least one gene critical to DNA repair through homologous recombination, including but not limited to: *ARID1A*, *ATM*, *ATR*, *MRE11A*, *NBN*, *PTEN*, *RAD50/51/51B*, *BARD1*, *BLM*, *BRCA1*, *BRCA2*, *BRIP1*, *FANCA/C/D2/E/F/G/L*, *PALB2*, *WRN*, *CHEK2*, *CHEK1*, *BAP1*, *FAM175A*, *SLX4*, *MLL2* or *XRCC*.
 - a. All patients must undergo NGS testing in a CLIA certified, CAP tested and bioinformatics-validated testing lab PRIOR to protocol treatment, to determine

which cohort they are eligible for – HRD versus HR proficient. The testing may have been done at any time prior to enrollment.

- b. For patients within whom a deleterious mutation in the homologous recombination pathway is found, the determination of a deleterious mutation must be supported in the documentation included in the testing, and should include clinical, or pre-clinical literature to support the finding that a specific mutation results in impaired function of the gene, and thus impaired DNA repair through homologous recombination. Variants of unknown significance will not be eligible.
 - c. Patients with germline deleterious mutations may have been identified at any time point prior to inclusion in the protocol and do NOT need to have this genetic testing repeated regardless of time frame and intervening therapy.
8. Participants must have received at least one line of therapy including a fluoropyrimidine and platinum drug. For participants with HER2+ tumors, they must have received trastuzumab. Adjuvant therapy does not count toward first-line therapy unless patient recurs within 6 months of completion.
 9. Have an Eastern Cooperative Oncology Group (ECOG) performance status of 0 to 1.
 10. Participants must have the ability to swallow whole pills and liquids at the Screening Visit and, in the investigator's judgement, for the duration of the study.
 11. Have adequate organ function as defined in Table 1

Table 1: Adequate Organ Function Laboratory Values:

System:	Laboratory Value:
Hematological	
Absolute neutrophil count (ANC)	$\geq 1500/\mu\text{L}$
Platelets	$\geq 100\,000/\mu\text{L}$
Hemoglobin	$\geq 9.0\text{ g/dL}$ or $\geq 5.6\text{ mmol/L}^a$
Renal	
Creatinine OR Measured or calculated ^b creatinine clearance (GFR can also be used in place of creatinine or CrCl)	$\leq 1.5 \times \text{ULN}$ OR $\geq 30\text{ mL/min}$ for participant with creatinine levels $> 1.5 \times \text{institutional ULN}$
Hepatic	
Total bilirubin	$\leq 1.5 \times \text{ULN}$ OR direct bilirubin $\leq \text{ULN}$ for participants with total bilirubin levels $> 1.5 \times \text{ULN}$
AST (SGOT) and ALT (SGPT)	$\leq 2.5 \times \text{ULN}$ ($\leq 5 \times \text{ULN}$ for participants with liver metastases)
Coagulation	
International normalized ratio (INR) OR prothrombin time (PT) Activated partial thromboplastin time (aPTT)	$\leq 1.5 \times \text{ULN}$ unless participant is receiving anticoagulant therapy as long as PT or aPTT is within therapeutic range of intended use of anticoagulants

ALT (SGPT)=alanine aminotransferase (serum glutamic pyruvic transaminase); AST (SGOT)=aspartate aminotransferase (serum glutamic oxaloacetic transaminase); GFR=glomerular filtration rate; ULN=upper limit of normal.

^a Criteria must be met without erythropoietin dependency and without packed red blood cell (pRBC) transfusion within last 2 weeks.

^b Creatinine clearance (CrCl) should be calculated per institutional standard.

Note: This table includes eligibility-defining laboratory value requirements for treatment; laboratory value requirements should be adapted according to local regulations and guidelines for the administration of specific chemotherapies.

12. Participant receiving corticosteroids, for reasons other than radiation related toxicities, may continue as long as their dose is stable (meaning no increase or on tapering dose) for least 4 weeks prior to initiating protocol therapy.
13. Female participants are eligible if they are: not pregnant (within 28 days prior to start of study treatment - see Appendix 3), not breastfeeding, and at least one of the following conditions applies:
 - a.) Not a woman of childbearing potential (WOCBP) as defined in Appendix 3
 - OR
 - b.) A WOCBP who agrees to follow the contraceptive guidance in Appendix 3 during the treatment period and for at least 120 days after the last dose of study treatment.
14. Male participants must agree to use a contraception as detailed in Appendix 3 of this protocol during the treatment period and for at least 120 days after the last dose of study treatment and refrain from donating sperm during this period.

5.2 EXCLUSION CRITERIA

An individual who meets any of the following criteria will be excluded from participation in this study:

1. Has received prior systemic anti-cancer therapy within 4 weeks or 5 half-lives (whichever is shorter) and has not recovered to grade ≤ 1 or baseline from AE associated with anticancer therapy prior to allocation.
 - a. Note: Participants must have recovered from all AEs due to previous therapies to \leq Grade 1 or baseline. Participants with \leq Grade 2 neuropathy may be eligible.
 - b. Note: If participant received major surgery within 4 weeks, they must have recovered adequately from the toxicity and/or complications from the intervention prior to starting study treatment.
2. Has received prior radiotherapy within 2 weeks of start of study treatment. Participants must have recovered from all radiation-related toxicities, not require corticosteroids specifically for radiation toxicities, and not have had radiation pneumonitis. A 1-week washout is permitted for palliative radiation (≤ 2 weeks of radiotherapy) to non-CNS disease.
3. Has received a live vaccine within 30 days prior to the first dose of study drug. Examples of live vaccines include, but are not limited to, the following: measles, mumps, rubella,

varicella/zoster (chicken pox), yellow fever, rabies, Bacillus Calmette–Guérin (BCG), and typhoid vaccine. Seasonal influenza vaccines for injection are generally killed virus vaccines and are allowed; however, intranasal influenza vaccines (eg, FluMist®) are live attenuated vaccines and are not allowed. Note: Vaccines for SARS CoV-2 will be permitted before and during the course of study.

4. Is currently participating in, or has participated in a study of an investigational agent or has used an investigational device within 4 weeks prior to the first dose of study treatment. Note: Participants who have entered the follow-up phase of an investigational study may participate as long as it has been 4 weeks after the last dose of the previous investigational agent.
5. Has a diagnosis of immunodeficiency or is receiving chronic systemic steroid therapy (in dosing exceeding 10 mg daily of prednisone equivalent) or any other form of immunosuppressive therapy within 7 days prior to the first dose of study drug.
6. Has a known additional malignancy that is progressing or has required active treatment within the past 3 years. Note: Participants with basal cell carcinoma of the skin, squamous cell carcinoma of the skin, or carcinoma in situ (e.g. breast carcinoma, cervical cancer in situ) that have undergone potentially curative therapy are not excluded
7. Has known active CNS metastases and/or carcinomatous meningitis that requires ongoing treatment or are found to be progressing. Participants with previously treated brain metastases may participate provided they are radiologically stable, i.e. without evidence of progression for at least 4 weeks by repeat imaging (note that the repeat imaging should be performed during study screening), clinically stable and without requirement of steroid treatment for at least 14 days prior to first dose of study treatment.
8. Has severe hypersensitivity (\geq Grade 3) to pembrolizumab or olaparib and/or any of its excipients.
9. Participant must not have impairment of gastrointestinal (GI) function or GI disease that may significantly alter the absorption of the study drugs (e.g., ulcerative diseases, uncontrolled nausea, vomiting, diarrhea, malabsorption syndrome, or small bowel resection).
10. Has active autoimmune disease that has required systemic treatment in the past 2 years (i.e. with use of disease modifying agents, corticosteroids or immunosuppressive drugs). Replacement therapy (eg., thyroxine, insulin, or physiologic corticosteroid replacement therapy for adrenal or pituitary insufficiency, etc.) is not considered a form of systemic treatment.
11. Has a history of (non-infectious) pneumonitis that required steroids or has current pneumonitis.
12. Has an active infection requiring systemic therapy.
13. Has a known history of Human Immunodeficiency Virus (HIV).

14. Hepatitis B (defined as Hepatitis B surface antigen [HBsAg] reactive) or Hepatitis C virus (defined as HCV RNA [qualitative] is detected) infection. Note: no testing for Hepatitis B and Hepatitis C is required unless mandated by local health authority.
15. Has active tuberculosis. Note: no testing for tuberculosis is required unless mandated by local health authority.
16. Has a history or current evidence of any condition, therapy, or laboratory abnormality that might confound the results of the study, interfere with the subject's ability to cooperate with the requirements of the study, or is not in the best interest of the subject to participate, in the opinion of the treating investigator.
- .
17. Is pregnant or breastfeeding, or expecting to conceive or father children within the projected duration of the study, starting with the screening visit through 120 days after the last dose of trial treatment.

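### Of the immune-related events for which Table 10 permanently stops pembrolizumab, section 5.2 names only pneumonitis as a history exclusion; a patient who recovered from another on earlier PD-1/PD-L1 therapy is kept out only by investigator judgement

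*Combined protocol and SAP*

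**What the plan says.** **Prior therapy.** Inclusion 8 requires at least one earlier line containing a fluoropyrimidine and a platinum. No criterion addresses earlier PD-1/PD-L1 therapy. Section 2.2 reports approvals of nivolumab and pembrolizumab with first-line chemotherapy and calls for trials in checkpoint-refractory disease.

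**History of immune-related events.** Item 11 of section 5.2 excludes a patient who "Has a history of (non-infectious) pneumonitis that required steroids or has current pneumonitis". Item 8 covers severe hypersensitivity "to pembrolizumab or olaparib and/or any of its excipients", which is a different kind of reaction.

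**Neighbouring criteria.**
- Item 1, note a: "Participants must have recovered from all AEs due to previous therapies to" Grade 1 or lower, or to baseline. It sets no limit on the worst earlier grade.
- Item 5: "Has a diagnosis of immunodeficiency or is receiving chronic systemic steroid therapy" above 10 mg prednisone equivalent a day, or other immunosuppression, in the 7 days before first dose.
- Item 9: "GI disease that may significantly alter the absorption of the study drugs".
- Item 10: "Has active autoimmune disease that has required systemic treatment in the past 2 years".
- Inclusion 11, Table 1: liver tests at entry, listed as "AST (SGOT) and ALT (SGPT").
- Item 16: any history or condition because of which it "is not in the best interest of the subject to participate, in the opinion of the treating investigator".

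**On study.** Section 7.2 makes unacceptable events under Appendix 6 a reason for mandatory discontinuation of treatment. Table 10 sets the grades at which pembrolizumab is withheld or permanently stopped.

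**The concern.** Item 11 shows that the sponsor accepts the principle that a resolved immune-related event can bar entry. The principle is applied to one organ only. For the other events that end pembrolizumab on study, the same history does not by rule prevent a patient from starting it.

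Patient safety is the main thing at stake: re-exposure to PD-1 blockade after, say, severe myocarditis or encephalitis on a drug of the same class, with the decision left to each investigator.

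The safety lead-in is a second reason to act. Under section 6.1.1 the DLT window runs to Cycle 2 Day 21, and pembrolizumab starts on Cycle 2 Day 1. A Grade 3 or 4 immune-related event on re-exposure in that cycle could count as a DLT, and more than 2 DLTs in 6 patients halts the study. The lead-in is meant to judge radiation with olaparib, so a recurrence of a known earlier reaction would blur that decision.

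**Working it through.** **The plan's own figure.** Section 9.2 gives 26 patients for an ORR of 0.25 against 0.45, one-sided alpha 0.1, power 0.8. With an exact binomial rule of at least 10 responses in 26, alpha is 0.0909 and power is 0.8064; 26 is the smallest number with alpha at most 0.10 and power at least 0.80. The figure reproduces, and nothing below changes it.

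**Table 10 against section 5.2.** The rows with a mandatory permanent stop are:

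| Table 10 row | What forces a permanent stop | Named history exclusion | Other criterion that touches it |
|---|---|---|---|
| Pneumonitis | Grade 3–4, or Grade 2 that recurs | Yes, item 11 | – |
| Diarrhea/colitis | Grade 4 | No | Item 9, if absorption is still affected |
| AST/ALT or bilirubin | Grade 3–4 | No | Table 1, current values |
| Myocarditis | Grade 2–4 | No | Screening ECG, with no eligibility threshold |
| All other immune-related events | Grade 4, Grade 3 that recurs, or events such as Guillain-Barré syndrome and encephalitis | No | None specific |

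Rows with a mandatory stop: 5. Named in section 5.2: 1. Not named: 5 − 1 = 4.

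Not counted: Grade 3–4 hypophysitis, hyperthyroidism and hypothyroidism, where Table 10 allows either withholding or stopping, and type 1 diabetes, where it only withholds. If the three optional endocrine rows are added, 7 of 8 are unnamed. The nephritis row shows only Grade 2 in the available text. A higher-grade line may have been lost in extraction, so it is left out.

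**One patient followed through the criteria.** Take a patient who had a fluoropyrimidine, a platinum and nivolumab first-line, developed Grade 3 myocarditis, recovered fully and has been off steroids for months.
1. Inclusion 8 (prior line): met.
2. Item 1, note a: met, because the event is now Grade 1 or lower.
3. Item 5 (7-day look-back) and inclusion 12 (stable steroid dose): not triggered.
4. Items 8, 9 and 11: not triggered.
5. Item 10: requires autoimmune disease that is active. A resolved drug reaction fits only by stretching the term. If item 10 did reach such events, item 11 would be largely redundant.
6. Item 16: the investigator may refuse, but need not.

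The same path holds for the other unnamed events once they have resolved.

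**A comparison inside the protocol.** One of the two routes to second-course pembrolizumab in Appendix 7 (after 35 administrations) is closed to patients who stopped for intolerability. Initial entry has no named counterpart for earlier PD-1/PD-L1 therapy.

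**The case against.** The strongest reply is that a safeguard exists and reaches history. Item 16 covers past conditions and past therapy in terms, and resolved severe myocarditis falls within it. Items 1, 5, 9 and 10, inclusion 12, Table 1 and the screening ECG also catch patients who are unrecovered, still on steroids or left with organ damage. This stands, and it makes the gap narrow. It does not close it, because for a fully recovered patient the outcome depends on who is asked.

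A reader might infer that Table 10 has already settled who may be re-dosed, so that entry contradicts the protocol. The documents do not support that. Appendix 6 concerns events arising under pembrolizumab on study, and section 6.5.2 applies the guidance when the investigator judges an event related to pembrolizumab or olaparib. No section extends it to a resolved event on an earlier agent.

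The count of one in five should not be pressed hard either. One row is a residual class that no single named condition could match, item 11 is wider than its own row because any steroid-treated episode excludes, and the nephritis row may be incomplete.

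A reader might also infer a flaw in the efficacy analysis, because PD-1-naive and PD-1-treated patients are mixed and prior PD-1 status is not a named factor in sections 9.1 or 9.4.1. That is not supported. Mixed enrolment is a legitimate choice and no objective claims activity in refractory disease. Prior treatment is reviewed and recorded (sections 6.5.1.1 and 8.1.1.3.2), and section 9.4.6 already summarises baseline characteristics, where this status could be shown.

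**Conclusion.** The point holds as a narrow eligibility gap worth closing because closing it is cheap. The criteria as written admit a patient who recovered from an event in four of the five mandatory-stop rows, unless an investigator chooses to refuse. This rests on three things: Table 10 as it reads in the available text, the ordinary meaning of active in item 10, and the inference that a reaction ending pembrolizumab on study is a sensible bar to starting it.

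The number of patients affected cannot be estimated. The documents give neither the share with earlier PD-1/PD-L1 therapy nor the rate of such events. A reader might try to supply both. Assuming 13 to 26 exposed candidates and a 1–5% event rate, the chance of at least one case, 1 − (1 − r)^m, runs from 1 − 0.99^13 = 12% to 1 − 0.95^26 = 74%. Both inputs are assumptions, and the result does not subtract patients already barred by item 11 or other criteria. It should not be read as the size of the gap.

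There is no error in the primary test, sample size, alpha or power. Naming prior PD-1 status in the reporting is optional.

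**What to change.** Add one item to section 5.2: *Had, on prior PD-1/PD-L1 therapy, an immune-related AE of a type and grade for which Appendix 6 Table 10 requires permanent discontinuation of pembrolizumab; endocrine events controlled on replacement therapy do not exclude.* The endocrine exemption agrees with item 10, which does not count replacement therapy as systemic treatment, and with Table 10's note allowing pembrolizumab to resume once such events are controlled.

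Cost: screening must capture the worst grade and any recurrence of earlier immune-related events. Sections 8.1.1.2 and 8.1.1.3.2 collect history and prior treatment but ask for neither. A small number of patients, which cannot be estimated from the documents, become ineligible.

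Optional: list prior PD-1/PD-L1 status (none / exposed / progressed on it) among the section 9.4.6 baseline characteristics and show ORR by it with exact 95% intervals, descriptively. These will be wide: 3 of 13 gives 5–54% and 1 of 5 gives 0.5–72%. Leave the primary test as it is.

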5.3 LIFESTYLE CONSIDERATIONS

5.3.1 MEALS AND DIETARY RESTRICTIONS

Participants should maintain a normal diet unless modifications are required to manage an AE such as diarrhea, nausea or vomiting. It is not recommended to consume grapefruit juice while on olaparib therapy.

5.3.2 CONTRACEPTION

Pembrolizumab and olaparib may have adverse effects on a fetus in utero. Refer to Appendix 3 for approved methods of contraception.

For this study, male participants will be considered to be of non-reproductive potential if they have azoospermia (whether due to having had a vasectomy or due to an underlying medical condition).

5.3.3 PREGNANCY

If a participant inadvertently becomes pregnant while on treatment with pembrolizumab and olaparib, it will be recorded as an AE and the participant will be immediately discontinued from study treatment. The site will contact the participant at least monthly and document the participant's status until the pregnancy has been completed or terminated. The outcome of the pregnancy will be reported to Merck within 2 working days if the outcome is a serious adverse

experience (e.g., death, abortion, congenital anomaly, or other disabling or life-threatening complication to the mother or newborn). The study investigator will make every effort to obtain permission to follow the outcome of the pregnancy and report the condition of the fetus or newborn to Merck. If a male participant impregnates his female partner, the study personnel at the site must be informed immediately and the pregnancy must be reported to Merck as an AE and followed as described in Section 8.4.7.

5.3.4 USE IN NURSING WOMEN

It is unknown whether pembrolizumab and olaparib are excreted in human milk. Since many drugs are excreted in human milk, and because of the potential for serious adverse reactions in the nursing infant, participants who are breast-feeding are not eligible for enrollment.

5.4 SCREEN FAILURES

Subject may be re-screened for eligibility with documented approval from the PI.

5.5 STRATEGIES FOR RECRUITMENT AND RETENTION

The volume of patients currently seen at the recruiting sites is sufficient to support required study volume. Physicians in medical oncology, radiation oncology, and surgery at each study site will be contacted via email to promote awareness of study recruitment.

6 STUDY INTERVENTION

6.1 STUDY INTERVENTION(S) ADMINISTRATION

Potential trial patients will be pre-identified at participating centers into two cohorts:

- (1) germline or somatic deleterious mutation involving genes critical to the DNA repair through homologous recombination deficiency (HRD), as demonstrated by Next-generation DNA sequencing in a CLIA certified, CAP tested and bioinformatics-validated testing lab prior to enrollment. This could include, but not be limited to one of the following genes: *ARID1A*, *ATM*, *ATR*, *MRE11A*, *NBN*, *PTEN*, *RAD50/51/51B*, *BARD1*, *BLM*, *BRCA1*, *BRCA2*, *BRIP1*, *FANCA/C/D2/E/F/G/L*, *PALB2*, *WRN*, *CHEK2*, *CHEK1*, *BAP1*, *FAM175A*, *SLX4*, *MLL2* or *XRCC* and
- (2) no evidence of HR deficiency.

If a pathogenic mutation in the HR pathway is confirmed and not listed above, the study PI will determine if the patient is eligible based on available clinical or pre-clinical literature.

[figure not shown]
The determination of a deleterious mutation must be supported in the documentation included in the testing, and should include clinical, or pre-clinical literature to support the finding that a

specific mutation results in impaired function of the gene, and thus impaired DNA repair through homologous recombination. Mutations and deletions will be evaluated against the Human Gene Mutation database and other online databases (ClinVar, Breast Cancer Information Core, PubMed) to evaluate the functional relevance, and to make a determination on the likelihood of the mutation resulting in defective homologous recombination-dependent DNA repair. Variants of unknown significance will not be eligible.

The testing may have been done at any time prior to enrollment.

Starting C1D1, olaparib 200mg PO BID will be given concurrently with radiation (25 Gy in 5 fractions). Each cycle is 21 days. Starting on C2D1, Pembrolizumab 200mg IV will be administered on Day 1 every 3 weeks with olaparib 300mg PO BID (12 hours apart). There is no specification regarding the sequence in which the drugs should be given on days when they are administered together. For Cycle 1, patients will be evaluated weekly for 3 weeks with blood tests, clinic visits, and physical exams. Starting Cycle 2, patient will be evaluated every 3 weeks on Day 1 of each cycle.

Patients will undergo serial tumor biopsies as depicted in the Trial Diagram below. Restaging will occur every 9 weeks. If at first restaging there is no evidence of progressive disease (PD), as determined by RECIST v1.1 and immune-related RECIST (irRECIST) criteria, and the patient is tolerating therapy, then patient will continue with study therapy, with clinic visits and lab work on Day 1 of future cycles and restaging imaging every 9 weeks. Patients will continue to remain on study as long as there is no evidence of PD (according to RECIST v1.1 and irRECIST criteria) and the therapy is adequately tolerated. For patients who demonstrate a response beyond 2 years of trial therapy, they will continue with olaparib treatment alone.

Serial tumor biopsies and blood samples will be taken to assess immune changes in tumor tissue and plasma at baseline compared to after combination SBRT/olaparib and after olaparib/pembrolizumab, assess response based on HRD status, PD-L1 expression, MMR/MSI, and TMB in tumor, changes in cytokines, ctDNA in plasma/serum

Patients will undergo the treatment and biopsy schedule as detailed above. However, in the event that tumor is inaccessible, the biopsy is not in the subject's best interest, or the patient refuses biopsy during course of the study, this will be documented and patients will be allowed to remain on study. Additionally, patients will continue to remain on study as long as there is no evidence of PD (according to RECIST v1.1 criteria and irRECIST) and the therapy is adequately tolerated. Interim analyses to assess secondary endpoints of OS and PFS will be scheduled to occur at 12 months and 24 months. For patients who demonstrate a response beyond 2 years of trial therapy, they will continue with olaparib treatment alone.

We plan to enroll 26 patients (13 HR deficient, 13 HR proficient).

